## 12.3 Response Criteria for Patients with Solid Tumors

See the table in [Section 8.0](#) for the schedule of tumor evaluations. Eligible patients must have measurable disease present at baseline and have had their disease re-evaluated after at least one dose of protocol therapy. In addition to the scheduled scans, a confirmatory scan should be obtained on the next consecutive cycle following initial documentation of objective response.

As outlined, patients will be assigned to one of the following categories for assessment of response: a) solid tumor (non-CNS) and measurable disease ([Section 12.4](#)); b) neuroblastoma with MIBG positive lesions ([Section 12.5](#)); c) CNS tumor ([Section 12.7](#)); and d) non-Hodgkin lymphoma/histiocytosis ([Section 12.8](#)). Note: Neuroblastoma patients who do not have MIBG positive lesions should be assessed for response as solid tumor patients with measurable disease.

Response and progression will be evaluated in this study using the revised Response Evaluation Criteria in Solid Tumors (RECIST) guideline (version 1.1). Key points are that 5 target lesions are identified and that changes in the *largest* diameter (unidimensional measurement) of the tumor lesions but the *shortest* diameter of malignant lymph nodes are used in the RECIST v 1.1 criteria.

### 12.3.1 Definitions

#### 12.3.1.1 Evaluable for objective response:

Eligible patients who receive at least one dose of protocol therapy will be considered evaluable for response. Evaluable patients who demonstrate a complete or partial response confirmed by central review before receiving non-protocol anti-cancer therapy will be considered a responder. All other evaluable patients will be considered non-responders.

#### 12.3.1.2 Evaluable Non-Target Disease Response:

Eligible patients who have lesions present at baseline that are evaluable but do not meet the definitions of measurable disease and have received at least one dose of protocol therapy will be considered evaluable for non-target disease. The response assessment is based on the presence, absence, or unequivocal progression of the lesions.

### 12.3.2 Disease Parameters

#### 12.3.2.1 Measurable disease: Measurable lesions are defined as those that can be accurately measured in at least one dimension (longest diameter to be recorded) as $\geq 20$ mm by chest x-ray, as $\geq 10$ mm with CT scan, or $\geq 10$ mm with calipers by clinical exam. All tumor measurements must be recorded in millimeters (or decimal fractions of centimeters).

Note: Tumor lesions that are situated in a previously irradiated area might or might not be considered measurable. If the investigator thinks it appropriate to include them, the conditions under which such lesions should be considered must be defined in the protocol.

#### 12.3.2.2 Malignant lymph nodes: To be considered pathologically enlarged and measurable, a lymph node must be $\geq 15$ mm in short axis when assessed by CT scan (CT scan slice thickness no greater than 5 mm). At baseline and in follow-up, only the short axis will be measured and followed.

#### 12.3.2.3 Non-measurable disease: All other lesions (or sites of disease), including small lesions (longest diameter $< 10$ mm or pathological lymph nodes with $\geq 10$ to $< 15$ mm short axis), are considered non-measurable disease. Bone lesions, leptomeningeal disease, ascites, pleural/pericardial effusions, lymphangitis cutis/pulmonitis, inflammatory breast disease, and abdominal masses (not followed by CT or MRI), are considered as non-measurable.

Note: Cystic lesions that meet the criteria for radiographically defined simple cysts should not be considered as malignant lesions (neither measurable nor non-measurable) since they are, by definition, simple cysts. 'Cystic lesions' thought to represent cystic metastases can be considered as measurable lesions, if they meet the definition of measurability described above. However, if non-cystic lesions are present in the same patient, these are preferred for selection as target lesions.

12.3.2.4 **Target lesions:** All measurable lesions up to a maximum of 2 lesions per organ and 5 lesions in total, representative of all involved organs, should be identified as target lesions and recorded and measured at baseline. Target lesions should be selected on the basis of their size (lesions with the longest diameter), be representative of all involved organs, but in addition should be those that lend themselves to reproducible repeated measurements. It may be the case that, on occasion, the largest lesion does not lend itself to reproducible measurement in which circumstance the next largest lesion that can be measured reproducibly should be selected. A sum of the diameters (longest for non-nodal lesions, short axis for nodal lesions) for all target lesions will be calculated and reported as the baseline sum diameters. If lymph nodes are to be included in the sum, then only the short axis is added into the sum. The baseline sum diameters will be used as reference to further characterize any objective tumor regression in the measurable dimension of the disease.

12.3.2.5 **Non-target lesions:** All other lesions (or sites of disease) including any measurable lesions over and above the 5 target lesions should be identified as non-target lesions and should also be recorded at baseline. Measurements of these lesions are not required, but the presence, absence, or in rare cases unequivocal progression of each should be noted throughout follow-up.

### 12.3.3 **Methods for Evaluation of Measurable Disease**

All measurements should be taken and recorded in metric notation using a ruler or calipers.

The same method of assessment and the same technique should be used to characterize each identified and reported lesion at baseline and during follow-up. Imaging-based evaluation is preferred to evaluation by clinical examination unless the lesion(s) being followed cannot be imaged but are assessable by clinical exam.

12.3.3.1 **Clinical lesions:** Clinical lesions will only be considered measurable when they are superficial (e.g., skin nodules and palpable lymph nodes) and  $\geq 10$  mm diameter as assessed using calipers (e.g., skin nodules). In the case of skin lesions, documentation by color photography, including a ruler to estimate the size of the lesion, is recommended.

12.3.3.2 **Chest x-ray:** Lesions on chest x-ray are acceptable as measurable lesions when they are clearly defined and surrounded by aerated lung. However, CT is preferable.

12.3.3.3 **Conventional CT and MRI:** This guideline has defined measurability of lesions on CT scan based on the assumption that CT slice thickness is 5 mm or less. If CT scans have slice thickness greater than 5 mm, the minimum size for a measurable lesion should be twice the slice thickness. MRI is also acceptable in certain situations (e.g. for body scans). Ideally, the same type of scanner should be used and the image acquisition protocol should be followed as closely as possible to prior scans.

**12.3.3.4PET-CT:** At present, the low dose or attenuation correction CT portion of a combined PET-CT is not always of optimal diagnostic CT quality for use with RECIST measurements. However, if the site can document that the CT performed as part of a PET-CT is of identical diagnostic quality to a diagnostic CT (with IV and oral contrast), then the CT portion of the PET-CT can be used for RECIST or International Pediatric non-Hodgkin Lymphoma Response Criteria measurements and can be used interchangeably with conventional CT in accurately measuring cancer lesions over time. Note, however, that the PET portion of the CT introduces additional data which may bias an investigator if it is not routinely or serially performed.

**12.3.3.5Tumor markers:** Tumor markers alone cannot be used to assess response. If markers are initially above the upper normal limit, they must normalize for a patient to be considered in complete clinical response.

**12.3.3.6Cytology, Histology:** These techniques can be used to differentiate between partial responses (PR) and complete responses (CR) in rare cases (e.g., residual lesions in tumor types, such as germ cell tumors, where known residual benign tumors can remain).

Cytology should be obtained if an effusion appears or worsens during treatment when the measurable tumor has met criteria for response or stable disease.

**12.3.3.7FDG-PET:** While FDG-PET response assessments need additional study, it is sometimes reasonable to incorporate the use of FDG-PET scanning to complement CT scanning in assessment of progression (particularly possible 'new' disease). New lesions on the basis of FDG-PET imaging can be identified according to the following algorithm:

- a. Negative FDG-PET at baseline, with a positive FDG-PET at follow-up is a sign of PD based on a new lesion.
- b. No FDG-PET at baseline and a positive FDG-PET at follow-up: If the positive FDG-PET at follow-up corresponds to a new site of disease confirmed by CT, this is PD. If the positive FDG-PET at follow-up is not confirmed as a new site of disease on CT, additional follow-up CT scans are needed to determine if there is truly progression occurring at that site (if so, the date of PD will be the date of the initial abnormal FDG-PET scan). If the positive FDG-PET at follow-up corresponds to a pre-existing site of disease on CT that is not progressing on the basis of the anatomic images, this is not PD.

**Note:** A 'positive' FDG-PET scan lesion means one that is FDG avid with an uptake greater than twice that of the surrounding tissue on the attenuation corrected image.

For patients with a positive PET scan at diagnosis, PET can be used to follow response in addition to a CT scan using the International Pediatric non-Hodgkin Lymphoma Response Criteria.

## 12.4 Response Criteria for Patients with Solid Tumor and Measurable Disease

### 12.4.1 Evaluation of Target Lesions

#### Complete Response (CR):

Disappearance of all target and non-target lesions. Any pathological lymph nodes (whether target or non-target) must have reduction in short axis to <10 mm. If immunocytology is available, no disease must be detected by that methodology. Normalization of urinary catecholamines or other tumor markers if elevated at study enrollment (for patients with neuroblastoma).

#### Partial Response (PR):

At least a 30% decrease in the sum of the diameters of target lesions, taking as reference the baseline sum diameters

#### Progressive Disease (PD):

At least a 20% increase in the sum of the diameters of target lesions, taking as reference the smallest sum on study (this includes the baseline sum if that is the smallest on study). In addition to the relative increase of 20%, the sum must also demonstrate an absolute increase of at least 5 mm. (Note: the appearance of one or more new lesions is also considered progressions). Note: in presence of SD or PR in target disease but unequivocal progression in non-target or non-measurable disease, the patient has PD if there is an overall level of substantial worsening in non-target disease such that the overall tumor burden has increased sufficiently to merit discontinuation of therapy

#### Stable Disease (SD):

Neither sufficient shrinkage to qualify for PR nor sufficient increase to qualify for PD, taking as reference the smallest sum diameters while on study

### 12.4.2 Evaluation of Non-Target Lesions

#### Complete Response (CR):

Disappearance of all non-target lesions and normalization of tumor marker level. All lymph nodes must be non-pathological in size (<10 mm short axis)

Note: If tumor markers are initially above the upper normal limit, they must normalize for a patient to be considered in complete clinical response.

Non-CR/Non-PD:

Persistence of one or more non-target lesion(s) and/or maintenance of tumor marker level above the normal limits

Progressive Disease (PD):

Appearance of one or more new lesions and/or *unequivocal progression* of existing non-target lesions. *Unequivocal progression* should not normally trump target lesion status. It must be representative of overall disease status change, not a single lesion increase.

12.4.3 Overall Response Assessment

Table 1: For Patients with Measurable Disease (i.e., Target Disease)

Target Lesions	Non-Target Lesions	New Lesions	Overall Response	Best Overall Response when Confirmation is Required*
CR	CR	No	CR	≥ 28 days Confirmation
CR	Non-CR/Non-PD	No	PR	≥ 28 days Confirmation
CR	Not evaluated	No	PR	
PR	Non-CR/Non-PD/not evaluated	No	PR	
SD	Non-CR/Non-PD/not evaluated	No	SD	documented at least once ≥ 28 days from baseline
PD	Any	Yes or No	PD	no prior SD, PR or CR
Any	PD**	Yes or No	PD	
Any	Any	Yes	PD	

\* See RECIST 1.1 manuscript for further details on what is evidence of a new lesion.

\*\* In exceptional circumstances, unequivocal progression in non-target lesions may be accepted as disease progression.

Note: Patients with a global deterioration of health status requiring discontinuation of treatment without objective evidence of disease progression at that time should be reported as "*symptomatic deterioration*." Every effort should be made to document the objective progression even after discontinuation of treatment.

Table 2: For Patients with Non-Measurable Disease (i.e., Non-Target Disease)

Non-Target Lesions	New Lesions	Overall Response
CR	No	CR
Non-CR/non-PD	No	Non-CR/non-PD*
Not all evaluated	No	not evaluated
Unequivocal PD	Yes or No	PD
Any	Yes	PD

\* 'Non-CR/non-PD' is preferred over 'stable disease' for non-target disease since SD is increasingly used as an endpoint for assessment of efficacy in some trials so to assign this category when no lesions can be measured is not advised

Table 3: Overall Response for Patients with Neuroblastoma and Measurable Disease

CT/MRI	MIBG	Bone Scan	Bone Marrow	Catechol	Overall
PD	Any	Any	Any	Any	PD
Any	PD	Any	Any	Any	PD
Any	Any	PD	Any	Any	PD
Any	Any	Any	PD	Any	PD
SD	CR/PR/SD	Non-PD	Non-PD	Any	SD
PR	CR/PR	Non-PD	Non-PD	Any	PR
CR/PR	PR	Non-PD	Non-PD	Any	PR
CR	CR	Non-PD	Non-PD	Elevated	PR
CR	CR	CR	CR	Normal	CR

#### 12.4.4 Overall Best Response Assessment

Each patient will be classified according to his “best response” for the purposes of analysis of treatment effect. Best response is determined as outlined in [Section 12.9](#) from a sequence of overall response assessments.

### 12.5 Response Criteria for Neuroblastoma Patients with MIBG Positive Lesions

#### 12.5.1 MIBG Positive Lesions

Patients who have a positive MIBG scan at the start of therapy will be evaluable for MIBG response. The use of  $^{123}\text{I}$  for MIBG imaging is recommended for all scans. If the patient has only one MIBG positive lesion and that lesion was radiated, a biopsy must be done at least 28 days after radiation was completed and must show viable neuroblastoma.

#### 12.5.2 The following criteria will be used to report MIBG response by the treating institution:

Complete response: Complete resolution of all MIBG positive lesions

Partial Response: Resolution of at least one MIBG positive lesion, with persistence of other MIBG positive lesions

Stable disease: No change in MIBG scan in number of positive lesions

Progressive disease: Development of new MIBG positive lesions

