## 8.2 Radiology Studies

8.2.1 **Central Radiology Review for Response:** Patients who respond (CR, PR) to therapy or have long term stable disease (SD) ( $\geq 6$  cycles) on protocol therapy will be centrally reviewed. The Operations center will notify the site when a patient has met the criteria for review. The tumor disease evaluations to be submitted for review include baseline (pre-study) evaluations as well as all end of cycle tumor disease evaluations which occurred while the patient was on the subprotocol therapy study.

8.2.2 **Technical Details of Submission:**

To ensure an adequate interpretation of FDG-PET and CT with contrast scans, scans transferred between the treating institutions and the Imaging and Radiation Oncology Core Group IROC RI (QARC) must be submitted in Digital Imaging and Communications in Medicine (DICOM) format. BMP files, JPG files, or hard copies (films) are unacceptable for adequate interpretation of PET and CT with contrast scans. Imaging studies must be submitted electronically as outlined in the following paragraph. The images will be made available to study radiologists and nuclear medicine physicians for central review.

Submission of Diagnostic Imaging data in DICOM format is required. Submission of the digital files and reports via TRIAD is preferred. Instructions for TRIAD set up are below.

Alternatively, the images and reports may be submitted via sFTP to IROC Rhode Island. Digital data submission instructions including instructions for obtaining a sFTP account, can be found at <http://irocri.qarc.org>. Follow the link labeled digital data. Sites using the Dicommunicator software to submit imaging may continue to use that application.

Corresponding Radiology reports may be submitted along with the electronic submission via TRIAD or sFTP or may be emailed to [[contact]](mailto:[contact]). The COG operations center and IROC are available to assist with any queries regarding the corresponding radiology reports which should be included when the scans are submitted

Questions may be directed to [[contact]](mailto:[contact]) or [contact].

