#### 12.5.3 The response of MIBG lesions will be assessed on central review using the Curie scale as outlined below. Central review responses will be used to assess efficacy for study endpoint. See [Section 8.2](#) for details on transferring images to the Imaging Research Center.

[figure not shown]
NOTE: This scoring should also be done by the treating institution for end of course response assessments.

The body is divided into 9 anatomic sectors for osteomedullary lesions, with a 10th general sector allocated for any extra-osseous lesion visible on MIBG scan. In each region, the lesions are scored as follows. The **absolute extension score** is graded as:

0 = no site per segment,

1 = 1 site per segment,  
2 = more than one site per segment,  
3 = massive involvement (>50% of the segment).

The **absolute score** is obtained by adding the score of all the segments. See diagram of sectors below:

The **relative score** is calculated by dividing the absolute score at each time point by the corresponding pre-treatment absolute score. The relative score of each patient is calculated at each response assessment compared to baseline and classified as below:

1. **Complete response:** all areas of uptake on MIBG scan completely resolved. If morphological evidence of tumor cells in bone marrow biopsy or aspiration is present at enrollment, no tumor cells can be detected by routine morphology on two subsequent bilateral bone marrow aspirates and biopsies done at least 21 days apart to be considered a **Complete Response**.
2. **Partial response:** Relative score  $\leq 0.2$  (lesions almost disappeared) to  $\leq 0.5$  (lesions strongly reduced).
3. **Stable disease:** Relative score  $> 0.5$  (lesions weakly but significantly reduced) to 1.0 (lesions not reduced).
4. **Progressive disease:** New lesions on MIBG scan.

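### Sites report neuroblastoma MIBG response by lesion count while the endpoint uses the Curie score, and the plan does not say which local result triggers confirmation and central review (minor)

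*Combined protocol and SAP*

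**What the plan says.** The references are to the combined protocol and SAP.

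- **Site rule, Section 12.5.2.** "The following criteria will be used to report MIBG response by the treating institution". The rule counts lesions. Partial response (PR) is "Resolution of at least one MIBG positive lesion, with persistence of other MIBG positive lesions". For stable disease (SD) the text is "Stable disease: No change in MIBG scan in number of positive lesions".
- **Endpoint rule, Section 12.5.3.** Each body segment is scored 0 to 3, and a 3 means that more than half the segment is involved. The relative score is the current total divided by the baseline total. PR is 0.5 or less; SD is above 0.5 up to 1.0. "Central review responses will be used to assess efficacy for study endpoint".
- **Site Curie scoring, NOTE in Section 12.5.3.** "This scoring should also be done by the treating institution for end of course response assessments".
- **Who is reviewed, Section 8.2.1.** Patients with CR or PR, and patients with SD for at least 6 cycles. The material reviewed includes baseline and every end-of-cycle evaluation. The section does not say whose assessment, or which MIBG rule, defines a response.
- **Stable patients, Section 11.5.** COG may ask for their scans; no rule is given for when.
- **Confirmation, Section 12.3.** Besides the scheduled scans, "a confirmatory scan should be obtained on the next consecutive cycle following initial documentation of objective response".
- **Default, Section 12.3.1.1.** Only a CR or PR confirmed by central review counts. "All other evaluable patients will be considered non-responders".

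**The concern.** The rule by which sites report MIBG response differs from the rule that decides the endpoint. The Curie score can fall because a lesion becomes less extensive; the lesion count falls only when a lesion disappears. A patient can therefore be a Curie partial responder and a site-reported stable patient on the same scan.

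This matters if the site report opens the door to confirmation and review. A patient who is not put forward, and whose scans are not requested, becomes a non-responder by default rather than by assessment. The NOTE does not settle it: it gives the site a second, possibly conflicting, result without saying which one is reported.

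There is also a structural case. Section 12.5.1 foresees patients with only one MIBG-positive lesion. Site PR requires other lesions to persist, so such a patient can be reported only as CR, SD or PD, however far the lesion shrinks.

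**Working it through.** **1. Can a Curie PR be a site SD?** Assume that no lesion resolves or appears and that no segment worsens. Let
- a = segments with one massive lesion that falls from 3 to 1,
- c = segments with several lesions that fall from 3 to 2,
- r1 and r2 = segments unchanged at 1 and at 2,
- d = segments unchanged at 3.

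Baseline B = 3a + 3c + r1 + 2·r2 + 3d. Follow-up F = a + 2c + r1 + 2·r2 + 3d. Curie PR needs 2F ≤ B, which reduces to a ≥ c + r1 + 2·r2 + 3d.

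- One massive lesion alone: 1/3 = 0.33. Curie PR, site SD.
- The same plus one unchanged single site: (1+1)/(3+1) = 0.50. Curie PR, site SD.
- A segment that only falls from 3 to 2: 2/3 = 0.67. Curie SD.
- A segment that falls from 2 to 1 has lost a site, so the site already reports PR.

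So discordance needs at least one segment with a single massive lesion that shrinks without resolving. It is possible, but narrow.

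**2. The reverse case.** If one of ten lesions resolves and the score goes from 14 to 13, the relative score is 13/14 = 0.93: site PR, Curie SD. This patient goes to central review and is corrected there. The cost is an unneeded confirmatory scan and a review, not an endpoint error.

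**3. When does it change overall response?** In Table 3 (neuroblastoma with measurable disease), CT/MRI SD gives overall SD whether MIBG is CR, PR or SD, so the discordance has no effect. It matters in Table 4 (MIBG-positive disease only), where MIBG PR or SD sets overall PR or SD when the other components show no progression. It also matters where CT/MRI has already responded: Table 3 gives PR if MIBG is PR, and has no row for CT/MRI response with MIBG SD. For patients followed by MIBG alone, Section 8.1 (note 4-C) does not require CT/MRI, so no second modality need catch the difference.

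**4. Can a responder be lost?** Scans fall after cycles 2, 4 and 6, then every 3 cycles (Section 8.1). Section 12.9 needs two consecutive determinations at least 3 weeks apart, before progression.
- *Curie PR after cycles 2 and 4, site SD both times.* The scans are 2 × 28 = 56 days apart, so this is a confirmed PR. If the patient leaves before 6 cycles of SD, Section 8.2.1 does not require review. The images exist, so a request under Section 11.5 could recover the response.
- *Curie PR after cycle 2, site SD, progression at the cycle 4 scan.* A reported PR would have called for a scan after cycle 3, 28 days later, and could have been confirmed before progression. Without that scan, progression falls on the second evaluation and best response is PD. Later review cannot recover this.

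**5. Size.** The plan's figure reproduces. Success is X ≥ 3, with X binomial and n = 20.
- At 5%: 1 − (0.3585 + 0.3774 + 0.1887) = 0.0755 (plan: alpha 10%).
- At 25%: 1 − (0.0032 + 0.0211 + 0.0670) = 0.9087 (plan: power 90%).

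Each missed responder lowers the observed rate by 1/20 = 5 percentage points. The number of affected patients is not given. Assuming 0 to 2 of 20, the range is 0 to 10 points, and this is an upper bound because it treats each of them as a missed responder. If k patients could never be counted, the same rule applies to n = 20 − k:

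| k | Type I error at 5% | Power at 25% |
|---|---|---|
| 0 | 7.5% | 90.9% |
| 1 | 6.7% | 88.9% |
| 2 | 5.8% | 86.5% |

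**The case against.** The strongest reply is that the plan largely covers this. Sites are asked for Curie scores at the end-of-course assessments. SD of at least 6 cycles is reviewed with all earlier evaluations, so an earlier Curie PR would be seen. COG can request scans of other stable patients. The study chair and MATCH leadership review study data weekly (Section 14.4.2). The discordant pattern is unusual, the exposed window is short, and the fusion-positive tumours named in Section 2.1 do not include neuroblastoma.

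Most of this stands, and it makes the point minor. It does not remove it. The NOTE does not say that the Curie result is the one reported, and the request route has no stated rule. The argument that routine scans can confirm a response covers the first case in step 4 of the working but not the second.

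A reader might infer that the lesion count definitely controls who is reviewed. The documents do not say so: Section 8.2.1 leaves open whose assessment defines a response, and a site that reported its Curie score would close the gap. A reader might also infer that every MIBG-avid patient is exposed; Table 3 rules that out where CT/MRI is SD.

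**Conclusion.** The point holds as a minor one. Sections 12.5.2, 12.5.3 and 8.2.1 do not say which local MIBG result is reported or triggers confirmation and review. Under the natural reading, a Curie partial responder can end as a non-responder. This requires all of the following:
- a massive lesion that shrinks without resolving;
- MIBG-only disease, or a CT/MRI response already in place;
- departure or progression before 6 cycles of SD;
- no request for the scans, or no second scan to confirm with.

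The cost is 5 percentage points of response rate per missed responder, for a number of patients that the documents do not give. The error is conservative: it lowers the observed rate and the power, and type I error falls rather than rises.

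Two stronger readings are not supported. One is that the primary decision is unreliable: even if one patient could never count, power would be 88.9% against 90.9%. The other is that expansion decisions are distorted. Expansion needs 3 responders in one histology (Section 11.3.2), and nothing in the documents suggests that many neuroblastoma patients; under the assumed 0 to 2 the question does not arise.

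**What to change.** State in Section 12.5.2 that the site's Curie category under Section 12.5.3 is the reported MIBG response. State in Section 8.2.1 that a site Curie relative score of 0.5 or less, or complete resolution of MIBG uptake, triggers the next-cycle confirmatory scan and central review. Overall response would still be read from Tables 3 and 4.

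The cost is a few lines of wording and, if the form does not already hold the score, one case report form field. Sites are already asked for the score, so no new scan type or reader is needed. The downside is a few extra confirmatory scans and central reviews, some for patients with CT/MRI SD whose overall response cannot change.
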